2.6 Data Collection

Participants will be invited to attend for assessments three times over the course of the project (baseline, end of intervention, further three months follow-up). It is expected that one hour to an hour and a half, will be needed for the physical assessments and completion of questionnaires. Participants will arrive at the baseline assessment session and informed consent taken, and a safety check will be made regarding their suitability for the physical assessments (health screening questionnaire, resting heart rate and oxygen saturation, and blood pressure). They will then complete the written questionnaires before undertaking the physical assessments in a structured sequence:

The following demographic details and information on health service use will be collected for all participants as the first part of an assessment questionnaire:

- Gender
- Age
- Ethnicity
- Marital status
- Employment/volunteer status

- Smoking status
- COPD diagnosis (date and severity)
- Details of PR attendance
- Co-morbid conditions
- Medication and health service use (use of inhalers and home oxygen, primary care consultations and hospital admission over the previous three months)
- Frequency and severity of exacerbations (over the previous three months)

Questionnaires

The quantitative data will be collected from both the singing group and the participants at baseline, and conclusion of the programme at three months, and on follow-up at six months. Participants will be asked to complete the following collection of questionnaires:

- COPD Assessment Test (CAT)
- MRC breathlessness scale (MRC)
- SF-36v2 (physical and mental health related quality of life)
- GAD-7
- PHQ-9

All of these questionnaires are simple, short and straightforward. It is anticipated that they will take 20 minutes to complete. Support will be available if participants need help in completing the questionnaires.

Exercise assessment and Spirometry

The following measures will be taken on the basis of physical examination:

- Weight and height (to allow for BMI)
- FEV1 (plus percentage)
- FVC (plus percentage)
- Expiratory pressure
- Chronic hypoxia and/or cor pulmonale
- Transfer factor for carbon monoxide (TLCO)

- Breathing patterns assessed with Structured Light Plethysmography (SLP) before and after the 6-minute walk test
- Exercise capacity assessed by 6-minute walk test (6MWT)

Procedure

On arrival participants will have a resting heart rate and oxygen saturation measurement using finger pulse oximetry and resting blood pressure to ensure good health to undertake the exercise test. On successful completion of this initial screening participants will then complete an initial SLP assessment followed by the a 6-minute walk test following published ERS / ATS guidelines, and then further assessment with SLP.

Six Minute Walk Test (6MWT)

The Six Minute Walk Test will be administered according to published guidelines (Holland, A.E. et al. (2014)). This will be conducted indoors to reduce the impact of weather and environmental conditions in a room with a level, non-slip surface. A shuttle walking course 10-metres in length will be measured out and marked with cones and masking tape. Distances walked (6MWD) will be measured to the nearest completed metre, with Borg breathlessness scores (0-10) and oxygen saturation and heart rate recorded at test termination using finger pulse oximetry and monitored for a minimum of 5-minutes post-exercise to ensure sufficient recovery. A number of parameters will be measured to reflect participant performance in this test (Table 6).

Table 6. Measurements derived from 6MWT	
Parameter	Description
Resting heart rate	beats per min ⁻¹ (bpm ⁻¹)
Resting oxygen saturation	SaO _{2rest} (%)
Resting blood pressure	mmHg
6-minute walk distance (6MWD)	metres (m)
Terminal exercise heart rate	bpm ⁻¹
Terminal exercise oxygen saturation	SaO _{2exercise} (%)
Exertional breathlessness	Borg breathlessness score (0-10)

Structured Light Plethysmography (SLP)

Participants will be assessed using SLP in a standardised (Hmeidi *et al.*, 2017) way before and after the 6MWT. In short, the participants will be asked to wear a tight white top and sit in front of the SLP device (Pneumacare Ltd. Cambridge UK). A chess board of light will be projected onto the participant's chest and abdomen. The participant will be instructed to sit still for 5 minutes. The measures in table 5 will be recorded and analysed are considered of potential interest to reflect patterns of breathing that may be affected by singing training. Consideration of such a large number of parameters is necessary and justified given the newness of this technique and the limited research so far conducted with COPD participants.

Parameter	Description
*mTi	Median inspiratory time (Ti) in seconds
*vTi	Interquartile range (IQR) of inspiratory time (Ti) in seconds
*mTi/Te	Median inspiratory time to expiratory ratio (Ti/Te)
*vTi/Te	Interquartile range (IQR) of inspiratory time to expiratory ratio (Ti/Te)
*mTi/Ttot	Median duty cycle (Ti/Ttot)
*vTi/Ttot	Interquartile range (IQR) of duty cycle (Ti/Ttot)
*mBreathPhase_RC2AB	Median asynchrony between ribcage and abdomen (also known as thoraco-abdominal asynchrony [TAA]) in degrees
vBreathPhase_RC2AB	Interquartile range (IQR) of asynchrony between ribcage and abdomen (also known as thoraco-abdominal asynchrony) in degrees
*mIE50	Median inspiratory flow divided by expiratory flow at 50% tidal volume (displacement)
*vIE50	Interquartile range (IQR) of inspiratory flow divided by expiratory flow at 50% tidal volume (displacement)
*mTPTEF_TE	Median time to reach peak tidal expiratory flow divided by expiratory time (tPTEF/tE)
*vTPTEF_TE	Interquartile range (IQR) of time to reach peak tidal expiratory flow divided by expiratory time (tPTEF/tE)

However, given the theoretical assumption that singing encourages a change in pattern of breathing towards greater engagement of the diaphragm in the production of longer, controlled out-breaths, the most discriminatory measure is considered to be a change in the 'mBreathPhase_RC2AB' parameter. An improvement on this measure would indicate better initiation of breathing utilising the diaphragm and a smoother breath cycle.

The key null hypothesis to be tested is that no change will be seen on the 'mBreathPhase_RC2AB' parameter as a result of regular singing at six months post-baseline assessment.

Qualitative Data

Participants in the singing groups will be asked to keep a weekly diary to record their use of the home programme of breathing and singing exercises. A representative sample of participants in both intervention and control arms of the trial will also be interviewed on completion of the final period of data collection.

Photography and filming

A photographic and film record will be made of the project as it progresses, and a representative sample of participants (including those in the control condition) will be interviewed on camera following the completion of data collection.

2.7 Randomisation

Following the assessments of the total sample at baseline, randomisation will be undertaken immediately, with stratification by sex and severity of COPD, and participants informed of their allocation. Use will be made of the 'Sealed Envelopes' professional randomisation service:

<https://www.sealedenvelope.com/>

2.8 Data Analysis

The design of the trial is a 3 by 2 mixed anova design with time as the within subjects factor at 3 levels (baseline, end of intervention and follow-up) and Condition as the between subjects factor with 2 levels (singing vs. control). The primary outcome variable for the trial will be the COPD Assessment Test score. Additional secondary analyses will consider a range of additional health measures, together with spirometry, exercise and SLP parameters. We will also examine differences between the intervention and control groups on indicators of service use to determine potential cost-savings associated with reduced inhaler usage, consultations with health professionals and hospital admissions. Embedded within the trial will be a qualitative assessment of the participant experience and perceived benefits, together with an evaluation of the resources to support practice between singing sessions.

Quantitative data

Quantitative data will be analysed using IBM SPSS 24. Comparative analysis will take place to examine composition of the intervention and control groups at baseline to assess equivalence. Comparisons will be made between the intervention and control groups at two follow up points to

determine whether the intervention has resulted in significant change on the primary and secondary outcome measures, which allow for rejection of the null hypothesis that singing results in no change in functional status, health related quality of life, mental wellbeing and patterns of breathing. Appendix 7.11 provides a plan for the statistical analysis to be undertaken, and considerations of effect size and power, provided by the project statistical consultant [name].)

Qualitative data

For the qualitative data obtained from individual interviews, thematic analysis (Braun and Clarke, 2006) will be used to identify any consistent themes. The qualitative data will be analysed using QSR International's NVivo 11 software. Within NVivo, queries will be run to determine word frequencies within respondents' qualitative comments.

For the thematic analysis, this process has six phases:

- Familiarising yourself with your data: Transcribing data (if necessary), reading and re-reading the data, noting down initial ideas.
- Generating initial codes: Coding interesting features of the data in a systematic fashion across the entire data set, collating data relevant to each code.
- Searching for themes: Collating codes into potential themes, gathering all data relevant to each potential theme.
- Reviewing themes: Checking if the themes work in relation to the coded extracts (Level 1) and the entire data set (Level 2), generating a thematic 'map' of the analysis.
- Defining and naming themes: Ongoing analysis to refine the specifics of each theme, and the overall story the analysis tells, generating clear definitions and names for each theme.
- Producing the report: The final opportunity for analysis. Selection of vivid, compelling extract examples, final analysis of selected extracts, relating back of the analysis to the research question and literature, producing a scholarly report of the analysis.

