1.6 Rationale and hypotheses for the current study

The conclusion of reviews of research supports the need for further research in the form of randomised controlled trials, as do the recommendations from the studies cited above. The proposed study will be larger than previous studies and include assessment of change on the primary outcome measure of COPD specific health status (the COPD Assessment Test, CAT), immediately after a three-month programme of regular singing, and on further three month follow up. The primary research null hypothesis will be that: 'No change occurs in COPD-specific health status, following ten weeks of regular, weekly singing at the primary end point for the trial six months post-baseline.'

A particular challenge is establishing real-time records of patterns of respiratory function to test a secondary hypothesis that regular singing leads to change towards deeper breathing supported by the diaphragm. One technique which may do this is structured light plethysmography (SLP) where movements of the chest wall and abdomen can be recorded for individuals as participants' breath. A small, feasibility exercise assessing the value of this technique for the current study has been undertaken (see above). The supplementary null hypothesis will be that: 'No changes occur in key parameters (specified below) derived from structured light plethysmography reflecting movement of the chest and abdomen during breathing, following three months of regular singing, at the primary end point of the trial six months post-baseline.'

Further secondary hypotheses will be tested for potential changes three months post-baseline at the conclusion of the singing programme.

Singing and COPD protocol version 1, 18 December, 2018

As, following randomisation, participants will inevitably be fully aware of their allocation to singing group or control, the trial cannot be double-blinded. However, in follow-up assessments, the staff conducting the measurement procedures will be blind to trial allocation.

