effect/analyses	expected difference	Notes	required N for minimum .80 power and alpha at .05 with moderate effect size d=.5		
anova - main effect of time	not relevant		34		
anova - main effect of condition	not relevant		86		
anova - interaction	significant		36		
anova - main effect of condition within T1	non significant		146	Bonferroni corrections included	sensitivity power analyses revealed that the minimum effect size detectable with power of .80 and sample size of 40 in each group is d=.68
anova- main effect of condition within T2	significant	the effect sizes of these two effects can be compared to test for prolonged effects of the intervention	146	Bonferroni corrections included	
anova - main effect of condition within T3	significant (but smaller than above)		146	Bonferroni corrections included	
anova - main effect of Time within Intervention Condition	significant		28		
anova - main effect of Time within TaU Condition	non significant		28		
anova - post hoc on main effect of Time within Intervantion Condition	significant between T1 and T2 but possibly disappearing between T2 and T3		39	Bonferroni corrections included	
anova - post hoc on main effect of Time within TaU Condition	not relevant		39	Bonferroni corrections included	

7.15 – Medway Singing and COPD Programme

The design of the singing programme is based on facilitator experience and participant feedback from singing for health projects conducted by the Sidney De Haan Research Centre over the past ten years. Each session will commence with physical and vocal warm-ups to prepare and protect the voice. These range in intensity and demand and are designed to provide a common focus, as well as encourage participants to learn to gain control of their breathing prior to singing.

Participants will be guided through a variety of songs, which gradually demand greater breath control and vocal production during the course of the singing sessions. Repertoire will include songs with short and long phrases, and a blended approach in each session will encourage confidence and breath-control. In addition, material will be utilised which encourages strong diction and vocal projection, both of which require consideration of breath control and management. Potential limitation in vocal range will be carefully addressed, with consideration given to the key and notation range in each song.

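### The six-month CAT comparison between arms is not named as the single primary test, and Appendix 7.14 puts it in a Bonferroni set with a baseline test that can only cost it power

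*Protocol*

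**What the plan says.** - **Protocol 1.6** places the primary hypothesis at six months and words the null as "No change occurs in COPD-specific health status, following ten weeks of regular, weekly singing at the primary end point for the trial six months post-baseline". No comparator appears in that wording. Hypotheses about three months are described there as further secondary ones.
- **Protocol 2.8** gives the model: "The design of the trial is a 3 by 2 mixed anova design with time as the within subjects factor at 3 levels". It adds: "Comparisons will be made between the intervention and control groups at two follow up points". Rejection of the null is tied to these comparisons, but neither follow-up point is singled out. The section sends the reader to Appendix 7.11 for the analysis plan, which is in fact printed as Appendix 7.14.
- **Appendix 7.14** has ten rows: two overall main effects, the interaction, the arm contrast at each of T1, T2 and T3, Time within each arm, and post hoc tests within each arm. The sample size column is headed "required N for minimum .80 power and alpha at .05 with moderate effect size d=.5". The row "anova - main effect of condition within T1" and its T2 and T3 counterparts each carry N = 146 with Bonferroni included, and a note gives a detectable d of .68 with 40 per arm. The row "anova - main effect of Time within Intervention Condition" is expected to be significant and the matching usual-care row is not. An expected result is given for most rows, but no row is said to decide the primary hypothesis.
- **Protocol 2.2** plans 40 evaluable participants per arm and refers to a two-tailed 5% level.

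**The concern.** A reader can work out from 1.6 and 2.8 that the deciding comparison should be singing against usual care on CAT at six months. No sentence says so, and the appendix that holds the analysis plan treats that comparison as one row among ten. There are two consequences.

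First, the six-month contrast shares its alpha with a baseline contrast. After randomisation the baseline null is true by design, so that test says nothing about singing. If it counts in the correction, the six-month test is run at about a third of the available alpha, in a trial that section 2.2 admits was sized by resources.

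Second, the interaction and the within-arm Time tests sit beside the T3 contrast with no ranking. They answer different questions. Because the null speaks of no change and names no comparator, a reader of the results could take either as the primary finding.

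**Working it through.** **Inputs.** From the protocol: 40 per arm (2.2); d = .5, power .80, alpha .05, N = 146 and detectable d = .68 (7.14); two-tailed 5% (2.2). Assumed, because the protocol gives no figure: equal correlation r between time points, taken as .5 and .7; SD 1 at every time point.

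**1. Reproduce the plan's figures.** For two arms of n, the t-test has noncentrality d × √(n/2) on 2n − 2 degrees of freedom. Taking the smallest N that gives power .80 at d = .5, and the d detectable with 40 per arm:

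| Alpha | Sides | Total N | Detectable d |
|---|---|---|---|
| .016 (.05/3 truncated) | one | 146 | .678 |
| .0167 (.05/3) | one | 144 | .674 |
| .0167 (.05/3) | two | 172 | .737 |
| .025 (.05/2) | two | 156 | .701 |
| .05 | two | 128 | .634 |

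Only the one-sided rows near .05/3 match 146 and .68. So T1 appears to be counted in the family. The figures are also one-sided, although 2.2 speaks of a two-tailed level.

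**2. Power at T3 with 40 per arm, d = .5, two-sided.** Noncentrality is .5 × √20 = 2.236 on 78 degrees of freedom.

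| Level | Critical t | Power |
|---|---|---|
| .05/3 (T1, T2, T3) | 2.447 | 42.1% |
| .05/2 (T2, T3) | 2.285 | 48.4% |
| .05 (T3 alone) | 1.991 | 59.8% |

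Removing T1 alone recovers about 6 percentage points. Making T3 the single primary test recovers about 18.

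**3. Effect of baseline adjustment.** Adjusting for baseline CAT reduces the residual SD by √(1 − r²). At .05 two-sided and d = .5, power becomes 72% (r = .5) to 87% (r = .7). Detectable d becomes about .634 × √.75 = .55 to .634 × √.51 = .45.

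**4. What the interaction tests.** With compound symmetry and n per arm, the 2-df interaction has noncentrality λ = (n/2) × Σ(δt − mean δ)² / (1 − r), where δt is the arm difference at time t.

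- Effect at T2 only, δ = (0, .5, 0): the sum of squares is .1667. λ = 20 × .1667/.5 = 6.67 at r = .5 and 20 × .1667/.3 = 11.1 at r = .7. Power is about 62% and 85%. Simulation gives 62 to 63% and 85%.
- Effect held to T3, δ = (0, .5, .5): the sum of squares is again .1667, so power is the same.

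The interaction therefore cannot tell an effect that has gone by six months from one that is fully kept. In the T2-only case the T3 contrast rejects in about 5% of trials at .05, and in under 2% at .05/3.

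**5. What the within-arm tests show.** If both arms drift equally by .25 SD from baseline and singing has no effect, Time within the singing arm is significant in 34% of trials (r = .5) to 53% (r = .7). The pattern that the appendix expects, singing significant and usual care not, appears in about 23 to 25%. These drift sizes are assumed. The pattern is rarer for smaller or larger drifts: at .5 SD it falls to 9% (r = .5) and 1% (r = .7).

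**The case against.** The strongest reply is that the protocol already points to the right comparison. Section 2.8 ties rejection to comparisons between the arms at follow-up, not to baseline and not to change within an arm. Section 1.6 fixes six months as primary and leaves three months to secondary hypotheses. The study question in 2.1 asks about benefit beyond usual treatment. This stands. What is missing is a designation, not the comparison itself.

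A reader might infer something stronger: that the plan will reject the six-month null wrongly, at the 62 to 85% rate of the interaction. The documents do not support that. Nowhere do they say that the interaction or a within-arm result decides the primary hypothesis. If the T3 contrast decides, the error rate is at or below 5%. A reader might also take "significant between T1 and T2 but possibly disappearing between T2 and T3" as the plan's own forecast that the effect on the arm difference will have vanished by six months. That row is a post hoc test within the singing arm, and it can equally mean that T2 and T3 do not differ because the gain is held. For the arm contrast at T3 the appendix expects a significant, though smaller, effect. The T2-only pattern is thus an illustration.

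Two further points are fair. The divisor of 3 is inferred from reproduced figures, not quoted. Bonferroni is also conservative, so it costs power and does not create false positives. On the one-sided basis that matches 146, power at d = .5 is 52 to 53% at about .05/3 and 72% at .05. The levels differ from the two-sided ones, but the loss is of similar size. Finally, this is a self-described pilot, which lowers the stakes. It does not remove the reason to name a primary test, since the protocol states a primary hypothesis and an intention to reject or retain it.

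**Conclusion.** The point holds as a failure of designation that has a cost in power. The protocol fixes the outcome and the time point and implies a comparison between arms. Neither 2.8 nor Appendix 7.14 names that comparison as the deciding test, and the appendix appears to run it at about .05/3 because a baseline test is in the set. At d = .5 with 40 per arm, two-sided unadjusted power is 42% where a single test would have 60%, and the detectable d is .74 where it would be .63. These figures rest on the inferred divisor and on a two-sided test as in 2.2. The interaction percentages rest on assumed correlations of .5 to .7. They show why that row should not be read as the primary result, and they are not the trial's false-positive rate. Nor is this a matter left to an unseen plan, because the analysis plan is printed as Appendix 7.14.

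**What to change.** - **1.6:** word the primary null as no difference between singing and usual care in CAT at six months.
- **2.8 and 7.14:** name the T3 difference between arms, adjusted for baseline CAT and reported with a 95% CI, as the single primary test at two-sided 5%, outside any Bonferroni set.
- **7.14:** delete the T1 significance test and describe baseline by arm instead.
- **2.8 and 7.14:** state that T2 is secondary, as 1.6 already implies.
- **7.14:** label the interaction and the within-arm rows as supportive or descriptive.
- **7.14:** replace 146 and .68 with two-sided figures for the single test. Unadjusted, these are N = 128 and d = .63. Figures adjusted for baseline should state the correlation that they assume.
- **2.8:** correct the cross-reference from Appendix 7.11 to 7.14.

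The cost is wording and a short recalculation. No participants, visits or data are added. The one downside is that T2 gives up any claim to be confirmatory.

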This information will help us assess in a controlled and rigorous way whether singing for people with COPD helps them to manage their breathing difficulties more effectively and contributes to feelings of improved quality of life and wellbeing. It will also enable us to evaluate the potential economic impacts of the initiative for the NHS.

1. Introduction

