2.1 Design, questions, aim and objectives

Design

The planned study is a single-blinded randomised controlled trial which will compare participation in a structured singing programme over 10 weekly sessions, with a usual treatment control. A 3 by 2 mixed anova design will be adopted with time as the within subjects factor at 3 levels (baseline, end of intervention and follow-up) and Condition as the between subjects factor with 2 levels (singing vs. control).

Questions

The study seeks to answer the following questions:

1. Is a ten-week progressively structured programme with recommended weekly practice between sessions acceptable, manageable and enjoyable for participants in the trial?
2. Does regular singing help to improve the perceived health and quality of life of patients with COPD over and above the provision of usual treatment?
3. Does regular singing result in a changed pattern of breathing in COPD patients with a shift towards breathing supported by the diaphragm, and a longer, slower controlled out-breath?
4. Does regular singing help patients with COPD manage the demands of daily living more effectively?
5. Does regular singing compared with usual treatment lead to a reduction in the use of medication and health services that will result reduced in care costs?

Aim and objectives

The overall aim is to conduct a pilot single-blinded randomised controlled trial, to evaluate the health benefits of a community singing group for patients with COPD in Medway, Kent. We are interested in finding out whether participating in community singing helps to improve the quality of life of patients with COPD.

Principal objectives are formulated around the primary outcome measure for the study, and a number of secondary outcomes. Service use will be assessed. There will also be an embedded qualitative study of patients' experiences of the singing programme, and the extent to which they follow guidance on practising breathing exercises and singing between group sessions.

Primary Outcome

- Impact on quality of life and management of breathing difficulties (as assessed by CAT) (Jones, et al., 2009; Kon, et al., 2014; Jones, et al., 2014; CAT, 2016)

Secondary Outcomes

- nMRC breathlessness scale (see: <https://mrc.ukri.org/research/facilities-and-resources-for-researchers/mrc-scales/mrc-dyspnoea-scale-mrc-breathlessness-scale/%EF%BB%BF> Williams, 2017; Fletcher et al., 1959)

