2.2 Participants

In this study, the participant population will come from the population of COPD patients supported by the Respiratory Service of Medway Community Healthcare. Participants will be recruited from patients who have received PR and those who are currently undergoing PR. The study will seek to achieve a final sample of 80 patients at the second follow-up – 40 in the intervention arm and 40 in the control arm. The intention is to recruit 100 patients who consent to allow for 20% attrition. It is expected that we will need to secure initial expressions of interest from at least 120 people to allow for drop out even prior to consenting.

The number of participants is based on the resources available to run the trial, and no formal power calculation has been used to determine the sample size to be recruited. There is an important ethical issue raised by running a trial that is potentially under-powered. As Freedman et al. (2001:401) put it:

Sample size and power must be addressed before the start of a randomised, controlled trial. It is necessary to know in advance the likelihood of finding valid conclusions from the population assessed. It may be acceptable to subject a patient to a chance of a less than ideal treatment, or to the psychological stress of being a 'subject', if there is a chance of a valid scientific outcome, but it is not ethical to conduct a study the design of which cannot make valid conclusions.

However, relevant considerations are:

- There is no reason to think that participation in the trial will pose any risks to the participants, nor subject them to 'less than ideal treatment' or undue psychological stress. All of our experience with running previous studies in East Kent and Lambeth and Southwark, and the feasibility study in Medway is that participants will find the singing intervention enjoyable and personally and socially beneficial.
-
- The Brompton trials (Lord, 2010, 2012), involved 28 and 24 participants respectively, and reported significant changes in the physical component of the SF-36. The proposed study will be three times larger.
-

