2.5 Intervention and control

Following baseline assessments, participants will be randomly allocated to the control arm, which will be treatment as usual (TAU) following PR, or the intervention group, which will be TAU plus group singing.

There will be two intervention groups in the same community venue in the Medway district meeting on different days. Each group will consist initially of approximately 25 participants at the outset. The groups will be conducted by two experienced and skilled singing facilitators who are trained in facilitating breathing and singing techniques specifically for people with a respiratory disease. A total of 10 sessions will occur over the period of the study, with the expectation that most participants will attend a minimum of 5 sessions. Each session will be run for 90 mins with breathing exercises and singing occurring for one hour. The additional time will allow for the groups to socialise. Details of the programme are given in Appendix 7.12 together with a goals framework with details the links between activities and expected outcomes.

To complement the group singing, intervention participants will also be expected to practise the taught techniques away from the group. This home practice will be supported by a guide and video resources developed specifically for people with COPD. Choir facilitators will encourage use of the resources each week and ask participants to keep a diary of their use of the home programme.

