4.2 Detailed timetable for assessments and the singing intervention

PLEASE NOTE: Sessions are proposed to start at the beginning of September 2019, to ensure that 10 sessions can be run before the middle of November. This will allow the post-intervention assessments to happen in November-December 2019. Easter 2020 is April 12.

May 2019

6 May bank holiday

- 13 Taster session
- 20 Taster session
- 27 May bank holiday

June 2019

- 3 Taster session
- 10 Taster session
- 17 Taster session
- 24 Taster session

July 2019

- 1 Consent and baseline assessments
- 8 Baseline assessments
- 15 Baseline assessments
- 22 Baseline assessments

August 2019

Randomisation and letters out to participants

September 2019

- 2 Session 1
- 9 Session 2
- 16 Session 3
- 23 Session 4
- 30 Session 5

October 2019

- 7 Session 6
- 14 Session 7
- 21 Session 8
- 28 Session 9

November 2019

- 4 Session 10
- 11 Start of follow-up assessments / and three-month break until mid-February

18 Follow-up assessments

25 Follow-up assessments

December

2 Follow-up assessments

9 End of follow-up assessments

16 Christmas break

23

30

January 2020

6

13

20

27

February 2020

3

10

17 Start of follow-up assessments

24 Follow-up assessments

March 2020

2 Follow-up assessments

9 Follow-up assessments

16 End of follow-up assessments

23 Data inputting and cleaning

30 Data inputting and cleaning

April-November 2020

Analysis, report writing, feedback to participants, publications

5. Project Finance

Core funding is provided by Oak Foundation and will be used as outlined below. Further support through staffing is provided by Canterbury Christ Church University, University of Kent and Medway Community Healthcare. The total cost of the trial is estimated to be £75K including contributions in kind (research staff, administration, university services etc.).

A letter from the funder confirming funds is attached to the IRAS application

Research support (e.g. £300 trial registration, Additional support for assessments)	2,000
Delivery of the intervention 14 sessions x 2 = 28 @ £250	7,000
Assessments (University of Kent) 100 participants x 3 assessments @ £50 each	15,000
Travel/subsistence/meetings	2,000
Materials/publicity	2,000
Contingencies	2,000
Total	30,000

6. References

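### The planned cost-saving figure is gross of the cost of delivering singing (about £100 per person) and should be labelled so, with a net figure reported beside it

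*Protocol*

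**What the plan says.** Protocol section 2.8 (Data Analysis) says that the arms will be compared on service-use indicators "to determine potential cost-savings associated with reduced inhaler usage, consultations with health professionals and hospital admissions". Research question 5 in section 2.1 has the same scope: it asks whether singing, compared with usual treatment, will "lead to a reduction in the use of medication and health services that will result reduced in care costs".

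The lay summary is broader. Of the information collected it says: "It will also enable us to evaluate the potential economic impacts of the initiative for the NHS".

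On what is delivered, section 2.5 states "A total of 10 sessions will occur over the period of the study", in two groups, and "Each group will consist initially of approximately 25 participants at the outset". The control arm receives usual treatment only. On cost, the budget in section 5 (Project Finance) has the line "Delivery of the intervention 14 sessions x 2 = 28 @ £250", which comes to £7,000. On who pays, the same section says "Core funding is provided by Oak Foundation and will be used as outlined below", with staffing support from two universities and the community healthcare provider. Section 3.5 expects groups that continue after the trial to be kept going by fund-raising or members' own contributions.

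**The concern.** The components of the cost result are named in section 2.8, and all of them are on the service-use side. Facilitated sessions are a resource that one arm uses and the other does not, so leaving them out can move the comparison in only one direction. Appendix 7.14 covers the mixed ANOVA and its sample sizes and has no economic content, so it does not widen the list. The service utilisation questionnaire in Appendix 7.12 collects service use only.

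The scope therefore fits question 5 but falls short of the lay summary. What is at stake is how the result is read. If the gross fall in service cost is smaller than the cost of the sessions, the report would show a saving although the service and the sessions together cost more than usual treatment. With no payer perspective stated for the cost analysis, a reader cannot tell which figure is meant.

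**Working it through.** **Inputs (all from the protocol)**
- Session rate £250; 14 sessions x 2 groups budgeted (section 5).
- 10 sessions per group described (section 2.5; the dated timetable in section 4.2 also lists 10).
- Two groups of about 25, so about 50 singers (section 2.5). This agrees with section 2.2: "The intention is to recruit 100 patients who consent to allow for 20% attrition", that is 50 per arm, with 40 per arm expected at the end.

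**Reproducing the budget**
- 14 x 2 = 28 sessions; 28 x £250 = £7,000, as implied by the line.
- 2,000 + 7,000 + 15,000 + 2,000 + 2,000 + 2,000 = £30,000, the stated total.

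**Delivery cost per person** = sessions per group x 2 x £250 / number of singers

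| Sessions per group | Total | Per person randomised (50) | Per completer (40) |
|---|---|---|---|
| 10 (as described) | £5,000 | £100 | £125 |
| 14 (as budgeted) | £7,000 | £140 | £175 |

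Per person randomised is the natural denominator, because sessions are paid for by the session and participants who drop out do not reduce the bill.

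**Gross and net**
- Gross = mean service cost (control) minus mean service cost (singing).
- Net = gross minus delivery cost per person randomised to singing.
- A gross figure between £0 and £100 (or £140) is a saving before programme cost and a net cost after it.

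**Rough scale (an assumption, for orientation only)**
- Section 1.1 gives a direct NHS cost of £810–930 million a year and 1.2 million people diagnosed: £675–775 per person per year, or about £338–388 over six months.
- Break-even fall at £100: 100/387.5 = 26% to 100/337.5 = 30%.
- Break-even fall at £140: 140/387.5 = 36% to 140/337.5 = 41%.

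The two national figures come from different sources and years, and trial patients may cost more than the average, which would lower these percentages.

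**The case against.** The strongest reply concerns the payer. A reader might infer that the analysis is biased in favour of singing, or that it would report a saving where the NHS pays more. The documents do not support that. No section says that the NHS pays for singing: in the trial the core funding is charitable, and later groups are expected to rely on fund-raising or personal contributions. If others pay, the service-use difference is the correct figure from the NHS side and nothing has the wrong sign. The difference is also a valid answer to question 5, which asks only about care costs, and section 2.8 calls the savings potential and names their source. It claims neither a net saving nor cost-effectiveness. All of this stands, and it limits the point to scope and labelling.

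A second reply is that perspective and costing detail are often left to a later analysis plan. That is true of unit costs and costing methods, and their absence is not criticised here. But the protocol itself lists what makes up the cost result, and that list is narrower than the aim in the lay summary.

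A third reply is that £140 is weakly founded, and this also stands. The protocol does not say what the four extra budgeted sessions per group are. Taster sessions before randomisation, or singing offered to controls after the last assessment, might account for some of them, and neither would be a singing-arm cost. Only £100 follows from the intervention as described.

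**Conclusion.** The point holds as a minor one. The planned cost result is gross of programme cost, is not labelled as such, and cannot by itself answer the aim in the lay summary. The omitted amount is about £100 per person randomised to singing, and at most £140 on the budgeted session line if all 14 sessions per group belong to the intervention.

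These amounts assume 50 singers and the £250 session rate. Materials, travel and contributions in kind lie outside that rate, so the full cost may be higher. A reported saving would be a net cost to the NHS only if the NHS commissioned the sessions; otherwise the cost falls on whoever funds them. The primary outcome (CAT) is not affected, and the trial describes itself as a pilot.

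**What to change.** In section 2.8:
- State the payer perspective of the cost analysis.
- Label the between-arm difference in service cost as gross of programme cost.
- Report beside it the net difference, after subtracting delivery cost per person randomised to singing, with a confidence interval. If delivery cost is treated as a fixed amount, the estimate and both limits simply shift by that amount.

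Before the unit cost is set, reconcile the 14 sessions per group in section 5 with the 10 in section 2.5, and say which sessions count as intervention.

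The change takes about two sentences and one subtraction, and needs no new patient data. The drawback is that the net figure will look less favourable to singing than the gross one.
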